## Methods

#### Design

A parallel grouped trial, with groups randomized 1:1 to either the intervention or control arms using a random number generator-based procedure applied at the time of inclusion.

The unit of analysis in the study is the RCS, and outcome measures are based on the difference in score (NEWS or composite outcome score) between the patient receiving an immediate ambulance response, and patients receiving a delayed ambulance response per dispatch log data.

## Setting

The study will take place in two EMDCs in central Sweden (Uppsala and Västmanland), serving a combined population of 499 000. The regions have a total of 32 ambulances during peak hours. Each dispatch center is staffed by 2-3 nurse call-takers and 1 ambulance director 24 hours per day. The

study has been piloted and initiated in the region of Uppsala, and Västmanland will join the study contingent on the collection of outcome data necessary to train and validate the risk assessment models.

In these regions during 2020, ca. 30% of callers received a high priority lights and sirens response, ca. 43% of patients received a low priority response, 5% were inter-facility transfers, and 22% of callers were referred to non-ambulance care. The median time from receipt of call to dispatch of ambulance (the "dispatch time") for low-priority ambulance responses was 18 minutes, and the median response time was 37 minutes. The dispatchers currently employ a self-developed, rule-based Clinical Decision Support System (CDSS) to structure patient interviews and determine a priority level, as described elsewhere (5,6).

## Eligibility criteria

Inclusion Criteria:

- Identification of a resource constrained situation by ambulance director (i.e., 2 or more patients awaiting an ambulance response)
- Assigned priority 2A or 2B (Low-priority ambulance response) by dispatch nurse call-taker
- Valid Swedish personal identification number collected at dispatch
- Age >= 18 years

#### Exclusion Criteria

- Relevant calls received more than 30 minutes apart
- Logistical factors (eg. the patients' geographical locations) affect the ambulance assignment decision
- On scene risk factors (eg. a patient is outdoors and risks hypothermia) or risk mitigators (eg. healthcare staff already on-scene with a patient) affect the ambulance assignment decision

#### Flow

Prior to initiation of the study, the risk assessment tool will be integrated into the dispatching interface used by all study centers. Ambulance directors will have overall responsibility for executing the study protocol, and be tasked with identifying RCS suitable for inclusion in the study.

Patients are included in the study upon the identification of an RCS involving eligible patients by the ambulance director at the point in time when an ambulance is available for immediate dispatch to one of the patients. Directors are instructed to carefully consider any non-clinical factors relevant to prioritizing the patients prior to randomization, and exclude any RCS where these factors would override a clinical determination per the above exclusion criteria. Upon selecting the relevant patients and pressing a button in the interface to compare the selected patients, the RCS will be randomly assigned to a study arm. In the control arm, the risk scores for each patient will be calculated and stored, but not displayed to the user. In the intervention arm, a mark will be displayed in the interface indicating which of the included patients has the highest risk score, along with a color-coded indicator of model confidence.

In both study arms, the ambulance director will confer with the nurses involved in triaging the patients to confirm which patient should receive the available ambulance. In the intervention arm, the ambulance director will note which patient was proposed by the machine learning framework in conference with the nurses. The director will then dispatch the available ambulance to the patient determined through this process to have the greatest need. This process will be repeated each time an ambulance becomes available.

#### Intervention

The intervention is based on a risk assessment instrument validated in a previous study. (1) Since the publication of the validation study, the risk assessment instrument been further developed to include free-text notes entered by dispatchers, which were found to improve the performance of the models. The full source code of the tool employed in the study is freely available for replication purposes: https://github.com/[name]/openTriage.

The framework estimates the likelihood that a patient will be assessed by ambulance crews to 1) have abnormal initial findings, 2) be transported to the hospital with lights and sirens, 3) receive a prehospital intervention, and 4) be admitted to the hospital, or die within 30 days. Hospital outcome measures are based on the first hospital visit within 72 hours to capture hospital visits of non-conveyed patients. The predicted likelihood for each of the outcomes is then combined into a composite risk score, with the above outcomes weighted 4:2:1:1. In each RCS included in the intervention arm, the patient with the highest composite risk score will be indicated in a user interface integrated in the Alitis dispatching system used in Uppsala and Västmanland. A graphical indicator of model confidence will be integrated in the user interface, notifying users as to whether the model has a high- or low level of confidence in the prediction, with a cutoff value calibrated to include ca. 50% of patients in each group.

Development of the modelling framework will be frozen upon initiation of the main study phase. New predictor and outcome data will however continue to be captured and used to update the models in a quarterly monitoring and model updating process to ensure patient safety.

#### Outcomes

The primary outcome of the study is based on the National Early Warning Score (NEWS) of each included patient based on the first set of vital signs captured by the ambulance crew upon arrival to the patient. If Ambulance vitals signs are missing (e.g., if a patient opted to take an alternate mode of transport to the hospital), the first set of vital signs obtained at ED triage will be used. NEWS was selected as the primary outcome of the study for two reasons: Firstly, NEWS is widely used in acute care, and has been thoroughly validated as being predictive of outcomes in a variety of adult patient cohorts.(7–10) Secondly, NEWS is based on patient vital signs, and is thus conceptually distinct from-, and prior in terms of causality to the outcome measures we employ to train the predictive models.

The latter reason is a subtle but important conceptual point which addresses two issues: Firstly, by selecting an evaluation measure which is not causally dependent on (or indeed identical to) the outcomes used to train the models, we minimize the possibility that assignment to the intervention or control arm in and of itself affects the evaluation measure (e.g., if it were communicated to the ambulance crew that a patient had a high risk of transport to the hospital using lights and sirens, this could influence the decisions of the crew, perhaps making them more likely to do so). Secondly, it addresses issues relating to AI system alignment. As suggested by the orthogonality thesis, the predictive performance of an AI system is independent of the goals of the system as a whole. (11) Operationalizing the need for a rapid ambulance response in terms of measurable outcomes is difficult, and we cannot assume that we have done so perfectly. Thus, it is appropriate that both the model and human decisions are evaluated in terms of a measure which in causally independent of either. In this way, we avoid giving the ML framework an unfair advantage over human dispatchers who may have internalized a different definition of patent risk and ambulance care need.

The first secondary outcome in the study is based on a composite score consisting of each of the four outcomes included in the risk assessment instrument. The outcomes will be weighted in a manner identical to the prediction framework. While this measure of intervention effectiveness suffers from

the problems noted above, this is the manner in which predictive models are typically evaluated.(3,4) Evaluating a measure of performance in terms of the goals the system was designed to achieve is thus also considered appropriate.

## Participant timeline

All outcome data are extracted algorithmically from ambulance and hospital databases, and the intervention occurs at a single point in time during the handling of the patient's call at the EMDC. As such, no follow up assessments involving the patient are required.

## Sample Size

Given the prevalence and diversity of non-clinical determinants in resolving RCS, the actual retrospective accuracy of dispatchers in identifying the most critically ill patients could not be determined. Instead, sample size was determined using a simulation-based approach. Low-priority calls are divided into 2 categories – 2A and 2B. A simulation was performed under the assumption that a priority 2A call would always be selected for immediate ambulance dispatch over a priority 2B call, and that dispatchers would have 100% compliance with the machine learning tool.

Based on 1000 bootstrap resampled pairs of patients ranked using either dispatch category or the ML framework, a U-statistic of 0.545 in favor of the ML framework was identified. This resulted in required sample size of 1500 at  $\alpha$ = 0.05,  $\beta$  = 0.85, and a randomization ratio of 1:1 for a Wilcoxon–Mann–Whitney test of difference in central tendency. (12) Based on an estimate of 2 RCS per day meeting all inclusion criteria, an upper bound on the data collection duration was set to 2 years.

Upon further refinement of the prediction models over the course of the pilot study, it was found that this difference-based test had an excess of power, and a more conceptually simple but less sensitive formulation of the primary hypotheses was adopted. Pilot study data indicate that RNs direct the available ambulance to the patient with the highest NEWS score 63.5% of the time (considering ties as "correct" assessments), while simulations suggest that the model will mark the patient with the highest NEWS correctly in 70.3% of cases, resulting in an estimated power of 0.8 at n=1500 using a two-sided test of proportions.

## Recruitment / Allocation

Patients will be recruited by ambulance directors upon identification of an RCS. Study arm allocation will be performed automatically by the server used to generate risk assessments using a simple random number generator implemented by the numpy python package.

## Blinding

Patients and ambulance crews will be blind to treatment arm allocation, but by the nature of the intervention, dispatchers will be aware of the randomization results. In extracting study data for final analysis, treatment group allocation will be assigned a randomized code to blind the analyst to treatment group assignment. All analyses will furthermore be performed using code made available for peer review and published along with the manuscript and will, insofar as possible, be written prior to final data extraction.

## Data management / Collection

Data collected by EMDCs regarding dispatcher decisions, machine learning model predictions, treatment group allocation, etc., will be stored in the currently employed dispatch system database used by both Uppsala and Västmanland to limit exposure of patient data. Database queries will be performed against this database, and combined with ambulance and hospital data collected in an

existing database used for quality assurance/improvement at Region Uppsala. Similar queries will be developed to extract ambulance and hospital data from Region Västmanland, and the need to develop these data extraction processes entails that Västmanland will begin including patients to the study after Region Uppsala. Manual data entry will be performed only to correct errors, and random spot-checks of data quality will be performed. These processes will be similar to those employed to generate the data used in the retrospective study validating the methods used here. (1)

## Statistical analysis

To generate risk predictions, gradient boosting models are applied to patient demographics, structured CDSS data, and free-text noted embedded using the bag-of-words method. The methods are implemented in the openTriage platform as the 'uppsala\_alitis' framework (13) and have been validated in previous research.

The primary hypotheses will be evaluated using a standard two-sided test of proportions between the intervention and control groups. Investigating the secondary hypotheses will involve comparing outcomes for the patient receiving an ambulance immediately with patients for whom dispatch is delayed. Patients who do not receive an ambulance immediately may also potentially be included in later trials. This induces a potential that information from intervention arm comparisons could be used by dispatchers in control arm comparisons, thus biasing the results in the direction of a smaller intervention effect. Steps were taken in the development of the user interface to limit these "spillover" effects.

Figure 1 – Analysis flow

Additional pre-specified analyses 1-2 will be investigated by assessing the compliance of dispatchers with the risk assessment tool of risk scores in the high and low confidence groups of the intervention arm (calibrated based on pilot study data to consist of ca. 50% of assessments each), as well as dispatcher compliance, with the hypothesis that compliance will be higher in the high-confidence group.

Pre-specified analyses 3-5 will be examined using time-series analysis within a regression framework employing a variable representing the study month as the independent variable of interest. Analysis 6 will be conducted by constructing calibration curves for the risk model based on the patient groups of interest.

Missing vital sign data will be imputed using Multivariate imputation by chained equations. (14) As we found previously that between-imputation variance after calculating NEWS scores was minimal, the median of 5 imputed NEWS values will be used to assess the primary hypothesis. An analysis of loss to follow-up (i.e., patients requesting to withdraw from the study) will be performed.

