#### TRIAL SIZE:

1500 RCS each consisting of multiple patients randomized 1:1 to control and intervention arms

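### The primary test uses no baseline covariates, although number of patients in the RCS, priority mix, centre and stored model scores are held for both arms; pre-specified adjustment would give a modest, low-cost gain in precision

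*Combined protocol and SAP*

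**What the plan says.** - **Primary test.** The Statistical analysis section specifies "a standard two-sided test of proportions between the intervention and control groups". It names no covariate, stratification factor or adjusted supporting analysis. Regression appears only for pre-specified analyses 3 to 5, with study month as the variable of interest. (Figure 1, the analysis flow, could not be read in the text available and is not relied on here.)
- **Allocation.** Recruitment / Allocation says arms are assigned "using a simple random number generator implemented by the numpy python package". No stratification is described.
- **Data held in both arms.** Under Flow, in the control arm "the risk scores for each patient will be calculated and stored, but not displayed to the user". Data management / Collection confirms that model predictions are kept in the dispatch database. Priority 2A or 2B is assigned by the call-taker before inclusion (Eligibility criteria). The director selects the patients before pressing the button that triggers randomisation, so number of patients and centre are also fixed by then. The scores are computed at that button press, but from call data that already exist, so they qualify as baseline.
- **Power.** Sample Size gives 0.8 at n=1500. Pilot data show that "RNs direct the available ambulance to the patient with the highest NEWS score 63.5% of the time", and simulations suggest that "the model will mark the patient with the highest NEWS correctly in 70.3% of cases".

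**The concern.** Whether the ambulance goes to the patient with the highest NEWS plausibly depends on features of the RCS that exist before allocation: how many patients compete, how far apart their predicted risks are, whether their priorities differ, and which centre is deciding. If these features predict the outcome, adjusting for them reduces the variance of the same risk difference without recruiting anyone.

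This matters somewhat more here because planned power is only 0.80 and uses the model's own hit rate as the intervention-arm rate, which implies that dispatchers always follow the tool. The Statistical analysis section also expects any spillover to shrink the observed effect. At stake is a small amount of power and interval width. The validity of the trial is not in question.

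**Working it through.** **Inputs from the documents.** Control rate 0.635 and intervention rate 0.703 (Sample Size); 1500 RCS at 1:1 (abstract, Trial size), so 750 per arm; two-sided test. Alpha of 0.05 is stated for the superseded Wilcoxon calculation and is assumed to carry over.

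**Step 1: reproduce the stated power.** Pooled z test, with d = 0.703 − 0.635 = 0.068 and mean rate 0.669.
- SE under the null = √(2 × 0.669 × 0.331 / 750) = 0.02430
- SE under the alternative = √((0.635 × 0.365 + 0.703 × 0.297) / 750) = 0.02424
- Power = Φ[(0.068 − 1.96 × 0.02430) / 0.02424] = Φ(0.84) = 0.7997

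The stated 0.8 is reproduced. The 95% CI half-width is 1.96 × 0.02424 = 4.75 percentage points.

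**Step 2: power with adjustment.** The documents give no R-squared for any RCS-level covariate, so a range is assumed. Effective n per arm = 750 / (1 − R²), put into the same formula.

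| Assumed R² | Effective total RCS | Power | CI half-width (points) |
|---|---|---|---|
| 0 | 1500 | 0.800 | 4.75 |
| 0.01 | 1515 | 0.804 | 4.73 |
| 0.03 | 1546 | 0.812 | 4.68 |
| 0.05 | 1579 | 0.820 | 4.63 |
| 0.10 | 1667 | 0.840 | 4.51 |

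**Step 3: what these R² values require.** For a binary covariate split 50/50, such as high or low model confidence, R² = s² / (4 × 0.669 × 0.331), where s is the difference in success rate between its two levels. A 10-point difference gives R² = 0.011. It takes about 21 points to reach 0.05 and about 30 points to reach 0.10.

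**Step 4: which part of the range is plausible.** RCS were simulated at about 63.5% and 70.3% success, with an assumed 10 to 35% of RCS having three patients (400,000 RCS per scenario). Adjustment was for number of patients and stored scores. The ratio of residual to raw variance was 0.97 to 0.98 in control and 0.945 to 0.956 in intervention. Weighting by the arm variances (0.635 × 0.365 = 0.2318; 0.703 × 0.297 = 0.2088):
- smaller gain: (0.98 × 0.2318 + 0.956 × 0.2088) / 0.4406 = 0.969
- larger gain: (0.97 × 0.2318 + 0.945 × 0.2088) / 0.4406 = 0.958

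The variance reduction is therefore about 3 to 4%. It is worth 1500 / 0.969 − 1500 ≈ 49 to 1500 / 0.958 − 1500 ≈ 66 RCS, with power 0.813 to 0.818. Centre and 2A/2B mix were not simulated.

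**Step 5: check by simulated trials.** 3000 trials of 1500 RCS per setting compared the raw z test with an augmented, logistic-model-standardised risk difference (Monte Carlo error about 0.7 points).

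| Covariate R² (AUC) | Raw power | Adjusted power |
|---|---|---|
| 0 (0.50) | 0.804 | 0.806 |
| 0.013 (0.57) | 0.798 | 0.806 |
| 0.05 (0.63) | 0.811 | 0.833 |
| 0.103 (0.69) | 0.802 | 0.841 |

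A useless covariate showed no loss of power.

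**Step 6: compare with incomplete compliance.** If 80% of the assumed gain is realised, the intervention rate is 0.635 + 0.8 × 0.068 = 0.689. Raw power is then 0.606, and adjustment at R² = 0.10 raises it only to 0.651.

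**The case against.** **The simple test was chosen knowingly.** Version History says the primary hypothesis was simplified for interpretability, and Sample Size accepts a less sensitive formulation because the earlier test had more power than needed. This explains replacing a rank test with a proportion. It gives no reason to leave out covariates: the adopted test has no spare power, and a standardised risk difference reads just as simply. What stands is that the headline analysis becomes slightly less simple.

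**The raw test is not wrong.** This stands in full. Chance imbalance is already in its standard error. For a covariate with 35% prevalence, the SD of the imbalance is √(2 × 0.35 × 0.65 / 750) = 2.5 points. With an assumed 10-point outcome difference, this moves the risk difference by about 0.25 points, against a CI half-width of 4.75. A reader might infer that the late entry of Västmanland biases the comparison. It does not, because allocation is 1:1 whenever an RCS is entered.

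**The predictors may be weak.** This also stands. A reader might infer strong prognostic value from the model's 70.3% hit rate. That figure shows how often the model ranks patients correctly. It does not show how well any RCS-level variable predicts a correct dispatch.

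**A stored score is not a stable covariate.** This stands and shapes the fix. Models are updated quarterly (Intervention), hyperparameters may be re-optimised (Monitoring), and Västmanland's entry is contingent on data to train and validate models (Setting). The scale of the score can therefore shift over time and between centres.

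**Conclusion.** The concern holds as a modest efficiency point. The plan's primary test is valid but unadjusted, and usable baseline information is held for both arms. Under an assumed R-squared of 0.01 to 0.10, power at 1500 RCS would be about 0.80 to 0.84. The most plausible range, 0.81 to 0.82, rests on the assumed mix of RCS sizes and simulated score behaviour described above. Only pilot data can settle the figure.

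Two stronger readings are tempting and unsupported. One is that the unadjusted test is an error; simple 1:1 randomisation makes it valid. The other is that adjustment would protect the trial's power. It would not: the larger exposure is the full compliance implied by using the model's own hit rate, and a realistic covariate gain recovers only a small part of what incomplete compliance would cost.

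**What to change.** Pre-specify as the primary analysis a covariate-adjusted marginal (standardised) risk difference with robust standard error, so that the estimand stays the difference in proportions.

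- **Covariates:** number of patients in the RCS; 2A/2B mix; centre, if Västmanland joins; and one score term, either the gap between the top scores or high/low confidence.
- **Score term:** define it so that it stays comparable across quarterly updates, for example standardised within model version.
- **Timing:** use pilot data to choose the covariates and estimate the gain, and fix them before any unblinding.
- **Interim looks:** state whether the quarterly Haybittle–Peto evaluations use the adjusted or the raw test.
- **Sensitivity analysis:** report the raw two-proportion test alongside.

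The cost is plan wording and a small amount of code, with no new data collection. The Blinding section already intends analysis code to be written, as far as possible, before final extraction. The downsides are a slightly less simple headline test and the care needed to define the score term.

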#### Hypotheses

Primary:

 The intervention results in a greater proportion of immediate ambulance responses in RCS being directed to the patient in the most critical condition as operationalized by subsequent NEWS value.

Secondary:

- The intervention improves differentiation with regards to a composite risk score consisting of ambulance interventions, abnormal initial ambulance findings, emergent transport, hospital admission, and mortality between patients receiving immediate vs. delayed ambulance response during RCS.
- 2. The intervention improves differentiation regarding NEWS between patients receiving immediate vs. delayed ambulance response during RCS.

Other pre-specified analyses:

- 1. Evaluation of overall personnel compliance with risk assessment instrument in intervention arm.
- 2. Evaluation of compliance in intervention arm cases where the model had a high vs low level of confidence.
- 3. Evaluation of improved/degraded compliance with risk assessment instrument over time as manifested by a slope change in a time series analysis of intervention group
- 4. Evaluation of spillover effects as manifested by a significant positive slope in a time series analysis of control group outcomes
- 5. Evaluation of change in risk assessment tool predictive value over time (covariate drift)
- 6. Evaluation of model calibration with regards to age, gender, and complaint category

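### Compliance analyses 1 and 2 lack a benchmark for agreement that would occur without the display, although the stored control-arm data could supply one

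*Combined protocol and SAP*

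**What the plan says.** Among the other pre-specified analyses under Hypotheses, item 1 is "Evaluation of overall personnel compliance with risk assessment instrument in intervention arm" and item 2 is "Evaluation of compliance in intervention arm cases where the model had a high vs low level of confidence". Item 3 looks for a "slope change in a time series analysis of intervention group". The Statistical analysis section carries out items 1 and 2 by "assessing the compliance of dispatchers with the risk assessment tool of risk scores in the high and low confidence groups of the intervention arm", "with the hypothesis that compliance will be higher in the high-confidence group". It names no test or significance level for them. Compliance is not defined; I read it as dispatch to the marked patient.

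The Flow section says: "In the control arm, the risk scores for each patient will be calculated and stored, but not displayed to the user". In the intervention arm the mark appears "along with a color-coded indicator of model confidence". The Intervention section sets that indicator "with a cutoff value calibrated to include ca. 50% of patients in each group", whereas Statistical analysis describes the same split as a share of assessments. Data management / Collection states that decisions, predictions and allocation are stored in the dispatch database. No readable passage uses control-arm agreement with the hidden mark as a comparator for compliance.

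**The concern.** In an RCS with two patients, a dispatcher who never looks at the mark will still send the ambulance to the marked patient at least some of the time. The Flow section describes no recording of the director's choice before the mark is shown, so the intervention arm alone cannot separate following the mark from coincidental agreement.

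Two readings are at stake. For analysis 1, a raw rate of, say, 80% may be taken to mean that the tool steered most decisions. For analysis 2, if clear-cut cases are the ones in which the model is confident, dispatchers may agree more often there without help. The directional hypothesis could then be met although nobody used the display.

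**Working it through.** **Plan's own figure.** The Sample Size section gives 63.5% (nurses, pilot data, ties counted as correct) and 70.3% (model, simulated), with power 0.8 at 1500 RCS. With 750 per arm and two-sided alpha 0.05 I obtain 0.7997, so it reproduces. No figure is given for compliance.

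**Assumptions.** Two patients per RCS; the 63.5% is unaided (the section says only that it comes from the pilot); an unknown share t of RCS tied on NEWS and counted as correct in both figures; 375 RCS per confidence group in the intervention arm (750/2).

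**Step 1: unaided agreement A if errors are independent given NEWS.** Accuracy among untied RCS is (p − t)/(1 − t), giving d for dispatchers and m for the model. With normally distributed latent risk rankings, their correlation is r = sin(π(d − 0.5)) × sin(π(m − 0.5)), and A = 0.5 + asin(r)/π. At t = 0: r = 0.4115 × 0.5954 = 0.245 and A = 0.579. A simpler formula that treats correctness as independent gives 0.635 × 0.703 + 0.365 × 0.297 = 0.555.

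| t | d | m | r | A | A at high / low confidence | chance hypothesis is met, display ignored |
|---|---|---|---|---|---|---|
| 0% | 0.635 | 0.703 | 0.245 | 0.579 | 0.626 / 0.533 | 73% |
| 5% | 0.616 | 0.687 | 0.198 | 0.563 | 0.600 / 0.526 | 54% |
| 10% | 0.594 | 0.670 | 0.149 | 0.548 | 0.576 / 0.519 | 35% |
| 15% | 0.571 | 0.651 | 0.100 | 0.532 | 0.551 / 0.514 | 18% |
| 20% | 0.544 | 0.629 | 0.054 | 0.517 | 0.528 / 0.506 | 8% |

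The last two columns take confidence to be the gap between the two risk scores, split at its median, and a two-sided 5% test of 375 against 375.

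**Step 2: shared information.** Independence is doubtful. The model uses structured CDSS data and the dispatchers' free-text notes (Intervention; Statistical analysis), and the nurses use the same CDSS (Setting). With r set directly to 0.3, 0.5 and 0.7, simulation gives A = 0.597, 0.667 and 0.747. Without ties, the marginal figures alone bound A only between 0.635 + 0.703 − 1 = 0.338 and 1 − (0.703 − 0.635) = 0.932.

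**Step 3: what raw agreement R implies.** If the display never turns agreement into disagreement, the share of otherwise discordant decisions that followed the mark is (R − A)/(1 − A). For R = 0.80:

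- A = 0.517: 0.283/0.483 = 0.59
- A = 0.579: 0.221/0.421 = 0.52
- A = 0.597: 0.203/0.403 = 0.50
- A = 0.667: 0.133/0.333 = 0.40
- A = 0.747: 0.053/0.253 = 0.21

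**Step 4: analysis 2 under other definitions of confidence.** If confidence is unrelated to the scores, the chance of meeting the hypothesis with the display ignored is 2.5%. If it reflects the marked patient's own score, the chance is about 26% at t = 0, falling to about 4% at t = 20%. If it is the score gap and r is 0.3, 0.5 or 0.7, agreement is 65% vs 54%, 76% vs 57% or 87% vs 62%, and the chance is 88% to above 99%.

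**Step 5: analysis 3.** Suppose true uptake is constant at 50%, and a share s of otherwise discordant control decisions follows remembered marks. The ratio of disagreement proportions (intervention/control) is 0.5/(1 − s), so apparent uptake is 50% at s = 0, 1 − 0.5/0.9 = 44% at s = 0.1, and 1 − 0.5/0.8 = 37.5% at s = 0.2. If spillover grows, a monthly between-arm contrast would show a decline that did not happen.

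**The case against.** The strongest reply is that items 1 and 2 ask how often the marked patient received the ambulance, and the intervention arm answers that. This stands. A reader might go further and infer that raw agreement cannot help explain a null primary result. The documents do not support that: the first sample-size simulation assumed 100% compliance, and one minus raw agreement measures departure from it directly, whatever the baseline. Model performance is followed separately, in analysis 5 and the quarterly reviews. What raw agreement lacks is the effect of the display on choice.

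A second reply is that every size above rests on unknowns: the tie rate, the number of patients per RCS, the confidence definition, and whether the pilot figure is unaided. This also stands. A reader might take 52-58% as the baseline or 73% as the error rate; each holds only under its stated assumptions. That one arm cannot separate the two components needs none of them.

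Third, the control arm is not clean. Statistical analysis concedes that information may pass from intervention to control comparisons. For a level, this makes the contrast conservative. For a trend, it can mislead (step 5), and a constant baseline creates no slope in the intervention arm. The documents therefore do not support the inference that analysis 3 is faulty, or that it should become a between-arm contrast.

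Finally, Figure 1 is not available to me, so a benchmark drawn there cannot be excluded.

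**Conclusion.** The point holds for analyses 1 and 2, as a minor one. Intervention-arm agreement is sound as description, but does not show how far the display changed choices. At 80% raw agreement, the share of otherwise discordant decisions following the mark could be anywhere from about 59% to 21% over the baselines considered. The high-confidence hypothesis could be met with the display ignored. The chance runs from 2.5% to about 73% under independence given NEWS, and higher with shared information. It cannot be narrowed further without a confidence definition and a tie rate. A reader might infer that the trial's main conclusions are at risk. They are not: the primary and secondary comparisons do not use these analyses.

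**What to change.** - Define compliance as dispatch to the marked patient, and state whether confidence is classified per patient or per assessment.
- Keep raw intervention-arm agreement as a description.
- Also report agreement with the hidden mark in the control arm, overall and by confidence group, using the model version and cutoff live at the time.
- Base any conclusion that dispatchers followed the tool, or followed it more at high confidence, on the between-arm contrast with a confidence interval. Report both the ratio of disagreement proportions and the difference, since the choice between them is one of scale.
- For analysis 3, show control-arm agreement by month beside the intervention-arm trend, as context only.
- State the limits: levels are conservative under spillover; reading one minus the ratio as uptake assumes the display never turns agreement into disagreement; and the indicator is shown with the mark and not randomised separately, so the contrast shows differential uptake, not the indicator's own effect.

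The cost is SAP wording and a check that control-arm confidence is stored or can be recomputed; no extra RCS are needed. Precision falls. Taking 80% agreement in the intervention arm and 55-75% in control, the 95% half-width of the between-arm difference is 4.2-4.6 points overall, against 1.96 × √(0.8 × 0.2/750) = 2.9 points for the raw rate. Within each confidence group it is 6.0-6.5 points. For high versus low confidence, the contrast of differences has a half-width of √2 times that, 8.4-9.1 points, against 1.96 × √(2 × 0.8 × 0.2/375) = 5.7 in one arm. Under score-gap confidence and 0-20% ties, the ratio contrast has power of about 58-68% to separate uptake of 50% from 30%, and 92-97% for 60% from 30%.
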